### **7.8.2      Laboratory data**

The analyses of laboratory data will be descriptive in nature and will be based on BI standards (8). If possible, analyses will be based on original values. If multiple reference ranges apply for a parameter (e.g. due to different age groups), analyses will be based on normalised values, which means transforming to a standard unit and a standard reference range.

Descriptive statistics of laboratory values over time and for the difference from baseline (see [Section 6.7](#)) will be provided. Frequency tables of changes between baseline and last value on treatment with respect to the reference range will be presented.

Possibly clinically significant abnormal laboratory values are only those identified either in the Investigator's comments or at the RPM/DBLM at the latest. It is the Investigator's responsibility to decide whether a lab value is clinically significant abnormal or not. Standard or project-specific rules for flagging clinically significant values in an automated manner will not be applied in this study.

Clinically relevant findings in laboratory data will be reported as baseline conditions (at screening) or as AEs (during the trial) if judged clinically relevant by the investigator, and will be analysed as such.

### **7.8.3      Vital signs**

The analyses of vital signs (blood pressure, pulse rate, body temperature) will be descriptive in nature. Descriptive statistics of vital signs over time and for the difference from baseline (see [Section 6.7](#)) will be provided.

Body weight will only be listed.

Clinically relevant findings in vital signs data will be reported as baseline conditions (at screening) or as AEs (during the trial) if judged clinically relevant by the investigator, and will be analysed as such.

### **7.8.4      ECG**

Abnormal findings in ECG will be reported as baseline conditions (at screening) or as AEs (during the trial) if judged clinically relevant by the investigator, and will be analysed as such. No separate listing or analysis of ECG data will be prepared.

### **7.8.5      Others**

Physical examination findings will be reported as relevant medical history/baseline condition (i.e., a condition already existent before intake of study drug) or as AE and will be summarised as such. No separate listing or analysis of physical examination will be prepared.

Matching pairs for subjects included in the      BI SC and      BI IV treatment group will be summarized in a table and a listing displaying the matching criteria.

#### **7.8.6 Local tolerability**

Local tolerability (absence or presence of "swelling", "induration", "heat", "redness", "pain", or "other findings") will be summarized with counts and percentages overall (i.e. over all time points) as well as by time point.

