	29	672:00	8:00	ambulatory visit	X	X			X		X	X 
	36	840:00	8:00	ambulatory visit	X							X
	43	1008:00	8:00	ambulatory visit	X							X
	57	1344:00	8:00	ambulatory visit	X							X 
	71	1680:00	8:00	ambulatory visit	X							X
	92 ±2	2184:00	8:00	ambulatory visit	X							X
	120 ±3	2856:00	8:00	ambulatory visit	X							X
	148 ±3	3528:00	8:00	ambulatory visit	X							
3	176 ±3	4200:00	8:00	EOT 	X 		X	X	X	X	X	X 

1. Screening with subject information, informed consent as the first measure, includes physical examination, check of vital signs, ECG, safety laboratory (under fasting conditions), pregnancy test, drug screening, demographics (including determination of body height and weight, smoking and alcohol history), relevant medical history, concomitant therapy and review of inclusion/exclusion criteria.
2. The time is approximate; procedures are to be performed and completed within 3 h prior to drug administration. Within 3 hours prior to the planned dosing, planned time -2:00 will be used.
3. Laboratory tests (safety laboratory) include clinical chemistry, haematology, coagulation and urinalysis; in addition at screening: serology (HBV, HCV, HIV), and drug screening.
4. PK sampling times may be adapted based on information obtained during trial conduct.
5. Standardized assessment of local tolerability only for subcutaneous injection using the criteria swelling, induration, heat, redness, pain or other findings.
6. If several actions are indicated at the same time point, the intake of meals will be the last action.
7. Confirmation of fitness includes physical examination.
9. At baseline, cytokine (IL1β, IL6, TNF-α and IFNγ) samples will be collected together with safety lab. Additional cytokine samples IL1β, IL6, TNF-α and IFNγ will be collected at 4 h and 24 h post-dose. Cytokine samples are only to be analysed from an individual subject in case of specific adverse events in this subject that are suggestive for a cytokine release. At 4 h and 24 h post-dose no safety lab needs to be taken.
10. Only drug screening and alcohol breath test.
11. AEs and concomitant therapies will be recorded throughout the trial, but will be specifically asked for at the time points indicated in the [Flow Chart](#) above.

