### **3.3.4.2 Discontinuation of the trial by the sponsor**

Boehringer Ingelheim reserves the right to discontinue the trial at any time for any of the following reasons:

1. New toxicological findings or serious adverse events invalidate the earlier positive benefit-risk-assessment. More specifically, the trial will be terminated if more than 50% of the subjects show drug-related and clinically relevant adverse events of moderate or severe intensity, or if at least one drug-related serious adverse event is reported that is considered to be unacceptable
2. The expected enrolment goals are not met
3. Violation of GCP, or the CTP, or the contract with BI by the trial site or investigator, disturbing the appropriate conduct of the trial
4. The sponsor decides to discontinue the further development of the investigational product
5. Dose escalation will be stopped if at least 2 subjects at one dose level show relevant individual QT prolongation, i.e. a QTc increase of greater 60 ms from baseline in connection with absolute QT or QTc greater than 500 ms, which has been confirmed by a repeat ECG recording

The investigator / the trial site will be reimbursed for reasonable expenses incurred in case of trial termination (except in case of the third reason).

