### **5.3 FURTHER ENDPOINTS**

#### **5.3.2 Safety parameters**

**CTP:**

*Safety and tolerability of the investigational drug will be assessed based on:*

- *Adverse events (including clinically relevant findings from the physical examination)*
- *Safety laboratory tests*
- *12-lead ECG*
- *Continuous ECG monitoring*
- *Vital signs (blood pressure, pulse rate)*
- *Local tolerability*
- *Oral body temperature*

Local tolerability will be assessed as absence or presence of "swelling", "induration", "heat", "redness", "pain", or "other findings".

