### **6.3 SUBJECT SETS ANALYSED**

The following subject sets will be defined for statistical analysis:

- Treated set (TS):  
This subject set includes all subjects who received study drug.
- Pharmacokinetic parameter set (PKS):  
This subject set includes all subjects of the TS who provide at least one observation for at least one primary or secondary PK endpoint without important PVs with respect to the statistical evaluation of PK endpoints, as defined in Section 7.3.1 and Section 7.3.2 of the CTP.

The discussion of all exceptional cases and problems and the decisions on the allocation of subjects to analysis sets will be made at latest at the RPM/DBLM.

Table 6.3: 1 Subject sets analysed

Class of endpoint	Subject set	
	TS	PKS
Disposition	X	
Exposure	X	
IPVs	X	
Demographic/baseline endpoints	X	
Other safety parameters	X	
PK endpoints		X

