## **7. PLANNED ANALYSIS**

The format of the listings and tables will follow the BI guideline "Reporting of clinical trials and project summaries" (001-MCG-159) ([10](#)).

The individual values of all subjects will be listed. Listings will generally be sorted by treatment group, subject number and visit (if visit is applicable in the respective listing). AE listings will be sorted by assigned analysis phase (see [Table 6.1: 1](#) for a definition of analysis phases). The listings will be contained in Appendix 16.2 (SDL) of the CTR.

The following standard descriptive statistical parameters will be displayed in summary tables of continuous variables:

N	number of non-missing observations
Mean	arithmetic mean
SD	standard deviation
Min	minimum
Median	median
Max	maximum

For plasma concentrations as well as for all PK parameters, the following descriptive statistics will additionally be calculated:

CV	arithmetic coefficient of variation
gMean	geometric mean
gCV	geometric coefficient of variation

The data format for descriptive statistics of plasma concentrations will be identical with the data format of the respective concentrations. The descriptive statistics of PK parameters will be calculated using the individual values with the number of decimal places as provided by the evaluation program. Then the individual values as well as the descriptive statistics will be reported with three significant digits in the CTR.

Tabulations of frequencies for categorical data will include all possible categories and will display the number of observations in a category as well as the percentage (%) relative to the respective treatment. Percentages will be rounded to one decimal place. The category missing will be displayed if and only if there actually are missing values. Percentages will be based on all subjects in the respective subject set whether they have non-missing values or not.

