## **7.8 SAFETY ANALYSIS**

All safety analyses will be performed on the TS.

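### The overall local-tolerability summary in SAP 7.8.6 is not limited to post-dose checks, so a sign seen only before the injection would count in it

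*SAP*

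**What the plan says.** Flow Chart footnote 5 in the protocol defines the assessment: "Standardized assessment of local tolerability only for subcutaneous injection using the criteria swelling, induration, heat, redness, pain or other findings". The mark stands at 16 time points in the adverse-event query column. The first is the Day 1, -2:00 row, which also carries footnote 2. Under footnote 2, "procedures are to be performed and completed within 3 h prior to drug administration".

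The SAP turns this into a binary variable. Section 5.3.2 states: "Local tolerability will be assessed as absence or presence of" each listed sign. Section 7.8.6 says that the signs "will be summarized with counts and percentages overall (i.e. over all time points) as well as by time point". It sets no post-dose limit and makes no comparison with the pre-dose finding.

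Three other rules bear on the table:

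- Protocol Section 7.3.3 assigns measurements planned before administration to screening, and leaves the detailed definition of these assignments to the SAP.
- SAP Section 6.1 defines screening and on-treatment phases for adverse events, safety laboratory data and vital signs. Local tolerability is not named.
- SAP Section 7 makes percentages relative to the respective treatment and adds: "Percentages will be based on all subjects in the respective subject set whether they have non-missing values or not".

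**The concern.** Local tolerability of the new SC formulation is a particular focus of the trial (protocol Section 2.1) and part of a named objective (Section 2.2). There is no placebo group (Section 3.2), so the check before dosing is the only within-subject reference for the injection site. A summary that pools this check with the later ones loses that reference and can count a finding that the injection could not have caused.

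The SAP handles other safety data differently. Section 6.7 defines baseline as the last measurement before dosing, and Sections 7.8.2 and 7.8.3 use it for laboratory data and vital signs. Section 7.8.6 does not. With 12 subjects planned per group, one subject moves the reported rate visibly.

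**Working it through.** The documents give no expected rate of local reactions, so there is no figure of the plan's to reproduce. The reaction counts below are assumptions for illustration.

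**1. Time points with footnote 5 (Flow Chart).** In hours relative to dosing: -2; 0.5, 4, 12, 24, 34, 48, 72, 96, 120, 144, 168, 336, 672, 1344 and 4200. That is 16 checks, 1 pre-dose and 15 post-dose.

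**2. Base of the percentage.** Protocol Section 7.5 plans 12 subjects per treatment group. SAP Section 7.8 says "All safety analyses will be performed on the TS", and SAP Section 6.3 defines the treated set: "This subject set includes all subjects who received study drug". Percentages are relative to treatment, so the base for an SC group is its injected subjects, planned as 12.

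**3. Effect on the overall rate.** Let *a* be the number of subjects with a finding at one or more post-dose checks, and *b* the number with a finding only at -2:00.

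- Overall rate as the SAP is worded: (*a* + *b*)/12
- Post-dose rate: *a*/12
- Difference: *b*/12, which is 8.3 percentage points per subject

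| *a* (assumed) | *b* (assumed) | SAP wording | Post-dose only |
|---|---|---|---|
| 2 | 0 | 2/12 = 16.7% | 16.7% |
| 2 | 1 | 3/12 = 25.0% | 16.7% |
| 2 | 2 | 4/12 = 33.3% | 16.7% |

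This counts subjects. SAP Section 7.8.6 does not say whether the overall count is of subjects or of assessments, but a percentage based on all subjects in the set points to subjects.

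**4. Signs that persist.** A sign present at -2:00 and still present after dosing is in *a* under either definition. A post-dose limit alone does not remove it, so such signs also need to be identified.

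**5. By-time-point base.** Let *r* be the subjects with a reaction at one visit and *m* the subjects not assessed then. The SAP reports *r*/12; the rate among those assessed is *r*/(12 - *m*). With *m* = 2 assumed:

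- *r* = 1: 1/12 = 8.3% against 1/10 = 10.0%
- *r* = 3: 3/12 = 25.0% against 3/10 = 30.0%

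Missed visits affect the overall figure only if a subject's reaction goes unobserved at every check.

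**The case against.** The strongest reply is that the plan, read as a whole, already separates the pre-dose check. Protocol Section 7.3.3 assigns it to screening, SAP Section 4 declares all analyses to be in accordance with the protocol, and SAP Section 6.7 makes it the baseline value. The by-time-point table would show -2:00 in its own row, individual values are listed, and a positive finding at an uninjected site in screened healthy volunteers is unlikely. The analysis is descriptive, with no hypothesis test.

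Most of this stands, and it limits the size of the problem. It does not settle the wording: Section 7.8.6 spells out its own definition of the overall figure, that definition takes in every time point, and the phase definitions in Section 6.1 omit local tolerability. If the protocol rule is intended, the SAP text contradicts it.

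On the by-time-point base, the SAP displays a missing category when values are missing, so a reader can recompute the rate. That makes it a minor point.

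Two stronger readings are tempting, but the documents do not support them.

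- A reader might infer that the overall rate is diluted because the treated set includes the intravenous subjects. It is not: percentages are taken within treatment, and every treated subject in an SC group was injected. The extra totals in SAP Section 6.1 are for adverse-event tables, and no pooled local-tolerability column is specified.
- A reader might infer that present/absent scoring leaves the termination criterion in protocol Section 3.3.4.2 without the intensity it needs. That criterion concerns "more than 50% of the subjects show drug-related and clinically relevant adverse events of moderate or severe intensity". Adverse events are graded for intensity under protocol Section 5.2.2.1 and tabulated by maximum intensity under SAP Section 7.8.1, and the synopsis counts clinically relevant local-tolerability findings among them. The checklist need not supply the grading.

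**Conclusion.** The point holds as a specific defect in one definition. As worded, the overall local-tolerability figure includes one pre-dose check out of 16 and does not follow the assignment rule in protocol Section 7.3.3. Each subject whose only finding is pre-dose adds 8.3 percentage points to an SC group's overall rate. The effect is zero if there is no such subject, and it is probably small.

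This rests on three assumptions: 12 treated subjects per SC group, an overall figure that counts subjects, and the placement of footnote 5 in the Flow Chart as read here. The by-time-point base is a secondary matter of presentation. The overall denominator within each SC group is appropriate.

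**What to change.** In SAP Section 7.8.6:

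1. Define the overall summary as the number and percentage of subjects in each SC group with at least one finding at any post-dose time point.
2. Show the -2:00 check separately as baseline.
3. Identify any sign already present at -2:00, so that a persisting sign is not read as a reaction to the injection. With present/absent data this can only flag the sign; it cannot show worsening.
4. Minor: give the number of subjects assessed at each time point and use it as the base for the by-time-point percentages, as a stated exception to the general rule in SAP Section 7.

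The cost is a few sentences of SAP text and the matching table programming. The -2:00 check is already scheduled, so no new data, CRF field or visit is needed.

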## **10. HISTORY TABLE**

Table 10: 1 History table

Version	Date (DD-MMM- YY)	Author	Sections changed	Brief description of change
Final	06-FEB-18	( ), )	None	This is the final TSAP without any modification
